#### Phase 2 Combination of ASP0739 + Pembrolizumab

Once safety lead-in is completed and 2 radiographic responses, complete response (CR) or partial response (PR), are observed by local or central review, the phase 2 combination cohorts may be opened in the respective tumor type where the responses were observed.

For R/R SS, initially 22 participants will be enrolled in an expansion cohort (stage 1). If the iORR does not meet the optimal stopping boundaries (see Section 6.9) for R/R SS, then an additional 38 participants (stage 2) may be enrolled for a total maximum sample size of 60. When the total number of participants reaches the maximum sample size of 60, it may be predicted that ASP0739 in combination with pembrolizumab is effective if the number of responses is greater than or equal to 18.

For R/R MRCL, initially, 22 participants will be enrolled in an expansion cohort (stage 1). If the iORR does not meet the optimal stopping boundaries (see Section 6.9) for R/R MRCL, then an additional 38 participants (stage 2) may be enrolled for a total maximum sample size of 60. When the total number of participants reaches the maximum sample size of 60, it may be predicted that ASP0739 in combination with pembrolizumab is effective if the number of responses is greater than or equal to 18.

For R/R ovarian cancer, initially, 10 participants will be enrolled in an expansion cohort (stage 1). If the iORR does not meet the optimal stopping boundaries (see Section 6.9) for R/R ovarian cancer, then an additional 19 participants (stage 2) may be enrolled for a total maximum sample size of 29. When the total number of participants reaches the maximum sample size of 29, it may be predicted that ASP0739 in combination with pembrolizumab is effective if the number of responses is greater than or equal to 4.

If both single agent and combination therapy expansion cohorts are open for the same tumor type, participants will be randomized to either single agent or combination therapy cohorts and the randomization ratio will be based on the number of open slots still available at each cohort.

### Replacement of Participants in Phase 2 Dose Expansion

If a participant in phase 2 is not response evaluable (defined as the response analysis set [RAS]), then an additional participant may be enrolled in that cohort based on sponsor discretion.

## **2.3 Randomization**

### Assignment and Allocation

Priority for enrollment will be given to the safety lead-in portion of the ASP0739 and pembrolizumab combination arm when both phase 2 single agent dose expansion and combination therapy safety lead-in are open.

If both single agent and combination therapy expansion cohorts are open for the same tumor type, participants will be randomized to either single agent or combination therapy cohorts and the randomization ratio will be based on the number of open slots still available at each cohort.

## **3 SAMPLE SIZE**

### ASP0739 Single Agent

A total of approximately 181 participants may be enrolled in single agent treatment.

#### *Phase 1 Single Agent Dose Escalation:*

The sample size of approximately 12 participants for the dose escalation phase is not based on a statistical power calculation. The number of participants enrolled will be dependent on the DLT incidence. The estimated number of participants, a minimum of 6 evaluable and up to 12, should provide adequate information for the dose escalation and safety objectives of the study.

#### *Phase 2 Single Agent Dose Expansion:*

It is estimated that up to approximately 169 participants may be enrolled in the single agent arms. The iORR is monitored using the BOP2 design.

For each indication (SS, MRCL or ovarian), with assumptions mentioned in the statistical hypotheses section below, the statistical power would be approximately at least 0.80 while controlling the type I error rate at 0.05 (1-sided).

The sample size of approximately 40 participants for other solid tumors known to express NY-ESO-1 is not based on statistical power calculation. A minimum of 10 participants per tumor type will be enrolled. If less than approximately 6 participants within each tumor type of melanoma, NSLCC-adenocarcinoma or squamous cell and ESCC are NY-ESO-1 positive based on analysis of the most recent tissue sample, additional participants may be added so that there are approximately 6 NY-ESO-1 positive participants.

### ASP0739 Combination with Pembrolizumab:

A total of approximately 158 participants may be enrolled in combination therapy.

*Combination Therapy Safety Lead-in:*

The sample size of approximately 6 to 9 participants for safety lead-in is not based on a statistical power calculation. The number of participants enrolled will be dependent on the DLT incidence. The estimated number of participants should provide adequate information for the safety objectives of the study.

*Phase 2 Combination Therapy:*

It is estimated that up to approximately 149 participants may be enrolled in the combination therapy arms. The iORR is monitored using the BOP2 design.

For each indication, with assumptions mentioned in the statistical hypotheses section below, the statistical power would be approximately at least 0.80 while controlling the type I error rate at 0.05 (1-sided).

Statistical Hypotheses:

*Phase 2 Single Agent (SS, MRCL, Ovarian):*

H0: iORR is 10%, at which the treatment is deemed as unacceptable.

H1: iORR is at least 25%, at which the treatment is deemed as acceptable.

*Solid tumors known to express NY-ESO-1 (melanoma, NSCLC-adenocarcinoma and squamous cell as well as ESSC):*

There is no formal statistical hypothesis for this cohort.

*Phase 2 Combination Therapy:*

*SS:*

H0: iORR is 20%, at which the treatment is deemed as unacceptable.

H1: iORR is at least 35%, at which the treatment is deemed as acceptable.

*MRCL:*

H0: iORR is 20%, at which the treatment is deemed as unacceptable.

H1: iORR is at least 35%, at which the treatment is deemed as acceptable.

*Ovarian:*

H0: iORR is 5%, at which the treatment is deemed as unacceptable.

H1: iORR is at least 20%, at which the treatment is deemed as acceptable.

## **4 ANALYSIS SETS**

In accordance with International Conference on Harmonization (ICH) recommendations in guidelines E3 and E9, the following analysis sets will be used for the analyses. Full Analysis Set (FAS) and Response Analysis Set (RAS) will be used for efficacy analysis. Safety Analysis Set (SAF) will be used for the analyses of safety variables. Pharmacokinetic Analysis Set (PKAS) will be used for pharmacokinetic analyses. Pharmacodynamics analysis

set (PDAS) will be used for all analyses of pharmacodynamics data. The data from all participants who were enrolled in the study will be included in the data listings. All enrolled participants are those who signed the informed consent form and were assigned a participant number.

For each dose level, the number and percentage of participants will be characterized for all treated participants and by each analysis set.

Population	Description
Enrolled	All participants who sign the informed consent form and are allocated to treatment.
Full Analysis Set (FAS)	All participants who are enrolled and receive at least one dose of study treatment.
Response Analysis Set (RAS)	The response analysis set will consist of all participants who are enrolled and receive at least one dose of IP and have at least one post baseline primary efficacy measurement.
Safety Analysis Set (SAF)	All participants who take at least 1 dose of IP.
Pharmacokinetic Analysis Set (PKAS)	The PKAS consists of the administered population for which pharmacokinetics data are available for at least one time point. Additional participants may be excluded from the PKAS at the discretion of the pharmacokineticist.
Pharmacodynamic Analysis Set (PDAS)	The PDAS will include the participants from the administered population for whom sufficient pharmacodynamic measurements were collected. The PDAS will be used for all analyses of pharmacodynamic data.
DLT Evaluation Analysis Set (DEAS)	
The DEAS is defined as all participants in SAF excluding participants who meet any of the following criteria:
 

• Participant is discovered to have enrolled without fully satisfying eligibility criteria.

• Participant received less than the planned dose in cycle 1 for reasons other than DLT.

• Participant has no DLT and withdraws from the study before the end of DLT evaluation period.

 
The DEAS will be used for the analysis of DLT data.

## 5 ENDPOINTS

The endpoints that are described in statistical methodology (Section 6) are described in this section.

### 5.1 Efficacy Endpoints

Tumor-related efficacy variables are evaluated by the Response Evaluation Criteria in Solid Tumors (RECIST) v1.1 and guidelines for response criteria for use in trials testing immunotherapeutics (iRECIST) (Seymour, L., et al., 2017).

### **5.1.1 Primary Efficacy Endpoints**

#### **5.1.1.1 Primary Efficacy Endpoint: Objective Response Rate per iRECIST (iORR)**

iORR is defined as the proportion of participants for each dose level whose best overall response is rated as confirmed complete response (iCR) or partial response (iPR) per iRECIST. Although iORR by independent central review is not included, other endpoints assessment will include:

- iORR with confirmed response by investigator assessment
- iORR with unconfirmed response by investigator assessment

### **5.1.2 Secondary Efficacy Endpoints**

#### **5.1.2.1 Secondary Efficacy Endpoint: Objective Response Rate per RECIST (ORR)**

ORR is defined as the proportion of participants for each dose level whose best overall response is rated as CR or PR per RECIST v1.1. The same analysis conducted for [Section 5.1.1.1 Primary Efficacy Endpoint: Objective Response Rate per iRECIST (iORR)] will be conducted for the endpoints of:

- ORR with confirmed response by investigator assessment
- ORR with unconfirmed response by investigator assessment

#### **5.1.2.2 Secondary Efficacy Endpoint: Disease Control Rate per iRECIST (iDCR)**

iDCR is defined as the proportion of participants for each dose level whose best overall response is rated as confirmed iCR, iPR or stable disease (iSD) per iRECIST.

#### **5.1.2.3 Secondary Efficacy Endpoint: Disease Control Rate per RECIST v1.1 (DCR)**

DCR is defined as the proportion of participants for each dose level whose best overall response is rated as confirmed CR, PR or stable disease (SD) per RECIST v1.1.

#### **5.1.2.4 Secondary Efficacy Endpoint: Overall Survival (OS)**

OS is defined as the time from the date of first dose until the date of death from any cause (death date – first dose date + 1). For a participant who is not known to have died by the end of study follow-up, OS is censored at the date of last contact (date of last contact – first dose date + 1).

**Table 1 OS Definition**

Situation	Date of Event or Censor	Outcome
Death before or on analysis cutoff date	Date of death	Event
Death after analysis cutoff date	Analysis cutoff date	Censor
Last known alive is before or on cutoff date	Last known alive date	Censor
Last known alive is after cutoff date	Analysis cutoff date	Censor

OS = Date of Event or Censor – Date of First Dose +1

### 5.1.2.5 Secondary Efficacy Endpoint: Progression-free Survival per iRECIST (iPFS)

iPFS is defined as the time from the date of first dose until death from any cause or radiographic disease progression assessed per iRECIST by investigator assessment.

If unconfirmed disease progression per iRECIST (iUPD) occurs but iSD, iPR, or iCR is observed any time subsequent to iUPD, iUPD status will be disregarded for determination of iPFS.

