**Table 2 iPFS Definition**

iPFS		
Situation	Date of Event or Censor	Outcome
No evaluable post-baseline imaging assessments, no death	Date of first dose (Day 1)	Censor
Participant did not receive new anti-cancer therapy (ACT):		
iCPD	First date where iUPD criteria are met	Event
No iCPD, but death recorded on eCRF	Date of death	Event
No iCPD nor death and not in one of the following cases : a) if the participant stops protocol treatment because they were not judged to be clinically stable, b) no further response assessments are done (because of participant refusal, protocol non-compliance, or participant death); c) the next timepoint responses are all iUPD, and iCPD never occurs;	Date of last radiological assessment	Censor
No iCPD nor death and is in one of the following cases : a) if the participant stops protocol treatment because they were not judged to be clinically stable, b) no further response assessments are done (because of participant refusal, protocol non-compliance, or participant death); c) the next timepoint responses are all iUPD, and iCPD never occurs;	First date where iUPD criteria are met	Event
Participant received new anti-cancer therapy (ACT):		
No progression before new ACT	Date of last radiological assessment before start of new anti-cancer therapy	Censor
iCPD before new ACT	First date where iUPD criteria are met	Event
iUPD before new ACT and not in one of the following cases: a) if the participant stops protocol treatment because they were not judged to be clinically stable, b) no further response assessments are done (because of participant refusal, protocol non-compliance, or participant death); c) the next timepoint responses are all iUPD, and iCPD never occurs;	Date of last radiological assessment before start of new anti-cancer therapy	Censor
Table continued on next page		

iPFS		
Situation	Date of Event or Censor	Outcome
iUPD before new ACT and is in one of the following cases : a)if the participant stops protocol treatment because they were not judged to be clinically stable, b) no further response assessments are done (because of participant refusal, protocol non-compliance, or participant death); c) the next timepoint responses are all iUPD, and iCPD never occurs;	First date where iUPD criteria are met	Event
Missed <math>\geq 2</math> scheduled radiological assessments		

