If last assessment prior to missing $\geq 2$ scans is iUPD	First date where iUPD criteria are met	Event
If last assessment prior to missing $\geq 2$ scans is not iUPD and no progression or death after missing $\geq 2$ scans	Date of last radiological assessment	Censor
No post-baseline tumor imaging prior to missing 2 scans and progression or death after missing $\geq 2$ scans	Date of first dose (Day 1)	Censor
No post-baseline tumor imaging prior to missing 2 scans and no progression or death after missing $\geq 2$ scans	Date of last radiological assessment	Censor
If radiographical progression or death occurs after missing 2 scheduled radiological assessments and last assessment prior to missing $\geq 2$ scans is not iUPD	Date of last radiological assessment before missing 2 scans	Censor

iPFS = Date of Event or Censor – Date of First Dose +1

Missing 2 scheduled imaging assessments:

Missing 2 scheduled imaging assessments is defined as the gap between two imaging assessments as more than 140 days (2.5 times the scheduled imaging assessment interval (2.5 x 56 days)). Imaging assessments after first iUPD will be excluded from PFS derivation.

Note: Participant cannot be censored at “NE”. If NE is the only previous assessment, then iPFS will be censored at Day 1.

To apply the cut-off date to iPFS is to exclude those tumor assessments after cut-off date and anti-cancer therapy date after cut-off date in the analysis.

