**Table 3 PFS Definition**

PFS		
Situation	Date of Event or Censor	Outcome
No evaluable post-baseline imaging assessments, no death	Date of first dose (Day 1)	Censor
Participant did not receive new anti-cancer therapy (ACT):		
Radiographical progression documented per RECIST v1.1	Date of radiological disease progression	Event
No radiographical progression, but death recorded on eCRF	Date of death	Event
Neither radiographical progression nor death	Date of last disease assessment	Censor
Participant received new anti-cancer therapy (ACT):		
Radiographical progression documented per RECIST v1.1 after new ACT	Date of last radiological assessment before start of new anti-cancer therapy	Censor
Radiographical progression documented per RECIST v1.1 before new ACT	Date of radiological disease progression	Event
No radiographical progression before new ACT but death recorded	Date of last radiological assessment before start of new anti-cancer therapy	Censor
No radiographical disease progression nor death	Date of last radiological assessment before start of new anti-cancer therapy	Censor
Missed >=2 scheduled radiological assessments		
If radiographical progression or death occurs after missing 2 scheduled radiological assessments	Date of last radiological assessment before missing 2 scans	Censor

PFS = Date of Event or Censor – Date of First Dose +1

Missing 2 scheduled imaging assessments:

Missing 2 scheduled imaging assessments is defined as the gap between two imaging assessments as more than 140 days (2.5 times the scheduled imaging assessment interval (2.5 x 56 days)). Imaging assessments after first iUPD will be excluded in PFS derivation.

Note: Participant cannot be censored at “NE”. If NE is the only previous assessment, then PFS will be censored at Day 1.

To apply the cut-off date to PFS is to exclude those tumor assessments after cut-off date and anti-cancer therapy date after cut-off date in the analysis.

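### The iUPD reset in SAP 5.1.2.5 has no end point and contradicts event rows in Table 2, and the SAP does not say which prevails

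*SAP*

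**What the plan says.** SAP 5.1.2.5 sets the reset rule for unconfirmed progression: if "iSD, iPR, or iCR is observed any time subsequent to iUPD, iUPD status will be disregarded for determination of iPFS". It sets no last assessment beyond which the reset stops.

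Table 2 then assigns event or censoring row by row. iCPD, with no new therapy or before it, is an event dated to the "First date where iUPD criteria are met". Without iCPD, an iUPD is still an event on that date in three listed cases:
- case a, "if the participant stops protocol treatment because they were not judged to be clinically stable";
- case b, no further response assessments;
- case c, "the next timepoint responses are all iUPD, and iCPD never occurs".

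The same three cases apply to participants who go on to new therapy, in the row that begins "iUPD before new ACT and is in one of the following cases". If none of the three applies, Table 2 censors. A separate block covers missed scans. Its first row, which opens "If last assessment prior to missing", makes an iUPD before two or more missed scans an event at the first iUPD date. Missing two scans is defined as a gap of more than 140 days.

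A note under Table 2 excludes imaging after the first iUPD from the PFS derivation. A near-identical note stands under Table 3, which defines RECIST v1.1 PFS. SAP 6.4.2.5 provides only for a listing of iPFS.

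**The concern.** The text looks forward without limit, while case a and the missed-scan row do not look forward at all. For a participant who meets one of those rows and later has a scan of iSD or better, the text removes the iUPD and the table keeps it as an event. Nothing in the SAP ranks the two. The event flag, and in some sequences the date, then depends on which was programmed.

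With new therapy there is also a problem of substance. A response to a different drug should not cancel a progression on ASP0739, and the literal reset allows that.

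**Working it through.** **Inputs.** Imaging interval 56 days, gap limit 2.5 intervals, and iPFS = date − first dose + 1, all from SAP Table 2 and its notes. The scan sequences are assumed for illustration.

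**The plan's own figure.** 2.5 × 56 = 140 days, as stated.

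**Scan days.** Weeks 8, 16, 24 and 32 fall on days 8×7+1 = 57, 16×7+1 = 113, 24×7+1 = 169 and 32×7+1 = 225.

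**Which rows conflict.** Case b has no later scan, so the reset cannot apply. Case c requires every later response to be iUPD, so it already contains the reset. Case a and the missed-scan row carry no condition on later scans. The conflict lies there.

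| Sequence | Table 2 | Literal reset |
|---|---|---|
| Missed scans: iUPD day 57, next and last scan iSD day 225 (gap 225 − 57 = 168 > 140) | event, day 57 | censored, day 225 (168 days later) |
| Case a, no new therapy: iUPD day 57, treatment stopped, last scan iSD day 113 | event, day 57 | censored, day 113 (113 − 57 = 56 days later) |
| Case a, new therapy day 70: iUPD day 57, iSD on the new drug day 113 | event, day 57 | censored, day 57 (last scan before new therapy) |
| New therapy day 70, none of cases a to c | censored, day 57 | censored, day 57 |

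In the second row, no Table 2 line strictly fits once the iUPD is disregarded, because the censoring line excludes anyone in case a. Censoring at the last scan is the nearest line. In the third row the status changes but the time does not. The fourth row shows that new therapy alone creates no conflict.

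**Event date after a valid reset.** Take iUPD day 57, iSD day 113, iUPD day 169, iCPD day 225. The text discards day 57, so the event falls on day 169. Read literally, "First date where iUPD criteria are met" gives day 57.

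**The note under Table 2.** If scans after the first iUPD are left out of iPFS, no later scan can reset an iUPD and the reset sentence has no effect. But iCPD also needs a later scan, so no iCPD could be observed and the iCPD rows would be empty. The note therefore cannot serve as the tie-breaker.

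**The case against.** **The impact is small.** iPFS is a secondary endpoint in a study that stopped early, and the SAP only lists it. This stands. A reader might infer that the conflict biases an iPFS curve upward, but the Kaplan-Meier analysis in Protocol 9.4.2.3 was not carried into the SAP, so no such estimate is planned.

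**The rule naturally stops at iCPD.** A reader might infer that a stable scan after confirmed progression cancels it. The documents do not support that. The sentence concerns unconfirmed progression, "iCPD before new ACT" has its own event row, and Protocol 7.1 schedules imaging only until iCPD. Stating the limit is still worthwhile, because the iCPD event is dated back to an iUPD.

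**Scans on new therapy are off schedule.** Follow-up visits end at new therapy (SAP 2.2). The Table 3 row "Radiographical progression documented per RECIST v1.1 after new ACT" censors before that therapy, so it handles such scans if they exist and does not plan them. This stands: the new-therapy conflict needs case a and an unscheduled scan. Case a without new therapy does not, because Protocol 7.1 continues imaging despite treatment interruption and through follow-up.

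**The missed-scan case needs a deviation.** Protocol 7.1 requires the confirmatory scan within 8 weeks. That is true, but Table 2 has this row precisely for such deviations.

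**The note settles it in favour of the table.** It points that way for status, but it names PFS rather than iPFS, and applied to iPFS it would hide iCPD.

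**Conclusion.** The reset sentence, Table 2 and the note beneath it cannot all be followed. The contradiction is confined to case a, with or without new therapy, and to iUPD as the last scan before at least two missed scans. It would be too strong to say that the reset erases these events: Table 2 still records them, so the result is undetermined. In the illustrations the status flips in all three conflicting sequences, and the time moves by 168, 56 and 0 days. How many participants are affected cannot be known from the documents. The consequence is limited to the event or censoring status and the date in the iPFS listing. It is a modest point, but in a terminated study the listing is the iPFS result.

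**What to change.** Before database lock:
1. Limit the reset in 5.1.2.5 to assessments made before iCPD and before the start of any new anti-cancer therapy.
2. State one rule, used in both text and table, for a later iSD, iPR or iCR in case a without new therapy, and another for such a scan after a gap of more than 140 days. Whether a scan after a long gap should reset the iUPD is open to judgement. If it may, Table 2 must also place the sequence iUPD, gap, iSD, later progression, which would otherwise fit no missed-scan row.
3. Define "First date where iUPD criteria are met" as the first iUPD that has not been reset.
4. Delete the note on imaging after the first iUPD under Table 2, or restrict it so that it does not apply to iPFS.

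The cost is a few phrases of SAP text and a small change to the iPFS derivation program. No new data are needed.
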